## 2.2. PART B (Cohorts 4-6)

Procedure	Screening (Up to 28 days before Day 1)	Study Period (Days)													Follow-up (14-21 days post last dose) / Early Withdrawal	Notes	
		-2	-1	1	2	3	4	5	6	7	8	9	10	11	12		
Outpatient Visit	X															X	
Admission to Clinical Unit		X															
Inpatient Stay at Clinical Unit			←-----X-----→														
Discharge from Clinical Unit																X	Following completion of all assessments.
Informed Consent	X																
Inclusion and Exclusion Criteria	X																
Demography	X																
Full Physical Examination	X																Additional exams/screens may be performed, or brief exams can be made into full exams, by the Investigator, as deemed necessary (e.g. where safety or laboratory findings indicate). Tests will be conducted within site specified standards.
Brief Physical Examination			X	X				X					X	X			
Drug/Alcohol/Smoki ng Screen	X		X														Tests include alcohol breath test, smoking breath test and urine drug screen.
Medical/Medication/ Drug/Alcohol History	X																
HIV, Hepatitis B and C Screening	X																
FSH + Oestradiol	X																Females only, if required
Holter Monitoring (48 hour)	X																

Procedure	Screening (Up to 28 days before Day 1)	Study Period (Days)													Follow-up (14-21 days post last dose) / Early Withdrawal	Notes		
		-2	-1	1	2	3	4	5	6	7	8	9	10	11	12	13		
Haematology/ Clinical Chemistry /Urinalysis Test	X		X		X		X		X		X		X		X		X	If trace protein is detected, a repeat test can be performed.  Sample to be drawn pre-dose on Days 2, 4, 6, 8 and 10.  Non-fasted samples can be collected on Day -1 and Follow-Up Visit. All other samples to be collected in fasted state.
Cortisol Test			X											X			Tests to be performed in the early morning on Day -1 and Day 11. If levels are <420 nmol/L, then a adrenocorticotropic hormone (ACTH) stimulation test will be performed to assess hypothalamic pituitary adrenal (HPA) axis.	
Safety biomarkers (KIM1, NGAL, Urinary albumin)				X				X									First urine sample of the morning to be collected (pre-dose). Additional samples may be collected, as deemed necessary by the Investigator (e.g. where safety or laboratory findings indicate).	
Telemetry				X	X												Continuous at least 24 hr post-evening dose. Initiate at least 15 min. prior to dosing.	
Randomization				X														
Study Treatment				X	X	X	X	X	X	X	X	X	X				BID dosing: GSK3186899 or placebo will be administered using a 12hr dosing interval. If a different dosing regimen is used, refer to Appendix 5 .	

Procedure	Screening (Up to 28 days before Day 1)	Study Period (Days)															Follow-up (14-21 days post last dose) / Early Withdrawal	Notes
		-2	-1	1	2	3	4	5	6	7	8	9	10	11	12	13		
12-Lead ECG	X		X	T	X		X		X		X		X		X	X	X	Vital signs to include HR, BP, temperature and respiration rate. BP will be conducted in both a supine and standing position if participant develops any signs/symptoms which in the investigators opinion are suggestive of adrenal insufficiency.
Vital signs	X		X	T	X	X	X	X	X	X	X	X	X	X	X	X	X	12-Lead ECG and Vital Signs to be conducted on Day-1 and pre-dose Day 1 and then at the subsequent time points post first-dose: 30 min, 1 hr, 1.5hr, 2hr, 2.5hr, 4hr, 6hr, 13hr and 14hr For Days 2-10: pre-dose assessments only.  Timings will be reviewed as cohorts progress and may be adjusted to ensure appropriate measurements relative to peak concentrations for subsequent cohorts  If a different dosing regimen is used, refer to Appendix 5 for alternative ECG and Vital Signs time-points.  T = Triplicate (for all assessments except temperature and respiratory rate).  If any abnormal ECG reading is recorded, refer to Section 8.1.6 for appropriate action.

Procedure	Screening (Up to 28 days before Day 1)	Study Period (Days)													Follow-up (14-21 days post last dose) / Early Withdrawal	Notes	
		-2	-1	1	2	3	4	5	6	7	8	9	10	11	12	13	
PK Blood sampling																	
PK samples will be collected pre-dose and at the following time points post first-dose:
 
Day 1: 10min, 30min, 1hr, 1.5hr, 2hr, 2.5hr, 3hr, 4hr, 5hr, 6hr, 8hr, 10hr, and 12hr
 
Days 2 – 9: Pre-dose PK samples collected for each dose
 
Day 10: PK samples will be collected pre-dose and at the following time points post first-dose: 10min, 30min, 1hr, 1.5hr, 2hr, 2.5hr, 3hr, 4hr, 5hr, 6hr, 8hr, 10hr, and 12hr.
 
The time points stated may be modified depending on emerging SAD PK profiles. If a different dosing regimen is used, refer to Appendix 5 for alternative PK blood sampling time-points.
 
Blood volumes to be collected include:
 
 
• 2 mL for post first-dose 0-11 hrs, and
 
• 5 mL for post first-dose 12-24 hrs (Days 1 and 10).
 

Urine Sampling (metabolism)													X	X			
A urine sample will be taken pre-dose (approx. 20mL). All urine from each participant will be collected from 0-24 hrs post dosing. Details of urine collection and processing are described in the SRM.

Procedure	Screening (Up to 28 days before Day 1)	Study Period (Days)													Follow-up (14-21 days post last dose) / Early Withdrawal	Notes	
		-2	-1	1	2	3	4	5	6	7	8	9	10	11	12	13	
Meals		X	X	X	X	X	X	X	X	X	X	X	X	X	X	X	If on fed regimen: On Day 1 through to D10, participants will receive an adapted standard meal 30 mins prior to dosing.  If on fasted regimen: On Day 1 through to D10, participants will have fasted 8hr overnight prior to dose 1. A breakfast will be served approximately 2hr after dose 1. Dinner will be served at least 2hr prior to dose 2. A snack may be consumed approximately 2hr after dose 2.  Participants will receive standardized meals scheduled at the same time in each period. If a different dosing regimen is used, refer to Appendix 5 for alternative meal times.  Meals will be served as per the site schedule on Days -1 and Days 11-13.  Water permitted on an ad lib basis up to 1hr before dosing. No water to be taken in the hour prior to dosing except for the liquid part of the adapted standard breakfast for the Fed regimen. At least 8 fl oz (240ml) to be taken 1 hour after dosing No water to be taken in the hour after dosing except for the rinse of the dose.
AE review		<=====X=====>													X		

Procedure	Screening (Up to 28 days before Day 1)	Study Period (Days)													Follow-up (14-21 days post last dose) / Early Withdrawal	Notes	
		-2	-1	1	2	3	4	5	6	7	8	9	10	11	12		
SAE review	X	←=====	=====X=====	=====→												X	
Concomitant medication review	X	←=====	=====X=====	=====→												X	

- The timing and number of planned study assessments, including safety, pharmacokinetic or other assessments may be altered during the course of the study based on newly available data (e.g., to obtain data closer to the time of peak plasma concentrations) to ensure appropriate monitoring.
- Any changes in the timing or addition of time points for any planned study assessments must be documented and approved by the relevant study team member and then archived in the sponsor and site study files, but will not constitute a protocol amendment. The IRB/IEC will be informed of any safety issues that require alteration of the safety monitoring scheme or amendment of the informed consent form (ICF).

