### Study Duration of Cohort 4-6

Screening	All screening assessments to be completed within 28 days prior to first-dose.
Treatment Period	Each Cohort will consist of a 10-day treatment duration (Days 1-10), with participants in-house for 14 nights and 15 days. Participants will be admitted to the unit the day before dosing (Day -2) and will remain in the unit overnight until Day 13, when they will be discharged after completion of all assessments.
Follow-up	At least 14 days and no greater than 21 days after last study drug administration. If warranted, additional follow-up visits may be scheduled.
Total duration	Approximately 8-9 weeks

**Data Monitoring Committee:** No

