### 3.3.1. Risk Assessment

Potential Risk of Clinical Significance	Summary of Data / Rationale for Risk	Mitigation Strategy
Investigational Medicinal Product (IMP) GSK3186899		
Kidney	
 
• Kidney tubule dilatation, which involved tubular epithelial cell loss, was noted in female rats given 400 mg/kg/day as spray dried dispersion (SDD), for 28 days (mean AUC 1290 µg.h/mL, mean Cmax 74.2 µg/mL on Day 28). This lesion is considered adverse in rats.
 
• These findings were associated with lower urine volume, with accompanying higher urine-specific gravity and lower urine pH, in females given 400 mg/kg/day.
 
• This lesion was not seen in 7-day rat studies nor in monkey toxicology studies of ≤21 days duration.
 
	
Inclusion/exclusion criteria:
 
 
• History of current or past significant renal diseases to be excluded.
 
• Screening eGFR (CKD-EPI) > 90 ml / min
 
• Urinary analysis at screening to be free of blood and protein. If trace protein is found, a repeat test will be performed within 24 hours
 
 
Monitoring:
 
 
• Serum Renal function and urinary analysis monitoring
 
• By observing the PK safety margin for renal findings of up to 3-fold (during the SAD part of the study) and up to 5-fold (during the MAD part of the study) for the total daily AUC and Cmax to be below the female rat NOAEL (AUC: 434 µg.h/mL, Cmax: 46.2 µg/mL).
 
 
Participant withdrawal
 
 
• New onset of any clinically significant and persistent haematuria / proteinuria (Spot Urine Protein Creatinine (UPC) ratio > 0.5) in the absence of another clinical explanation e.g. calculus / infection.
 

Potential Risk of Clinical Significance	Summary of Data / Rationale for Risk	Mitigation Strategy

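### Part B schedules its kidney-injury markers only before dosing on Days 1 and 5, so there is no planned end-of-dosing reading over the 10-day course

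*Protocol*

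**What the plan says.** - **Biomarkers.** Protocol 2.2 has a row for "Safety biomarkers (KIM1, NGAL, Urinary albumin"), marked on Days 1 and 5. The row's note reads "First urine sample of the morning to be collected (pre-dose"), and adds that "Additional samples may be collected, as deemed necessary by the Investigator", for example when safety or laboratory findings point that way. Appendix 5 leaves this row unchanged if once-daily or three-times-daily dosing is chosen.
- **Dosing.** "Each Cohort will consist of a 10-day treatment duration (Days 1-10"). For the planned regimen, "GSK3186899 or placebo will be administered using a 12hr dosing interval". Participants stay in the unit until Day 13 and return 14 to 21 days after the last dose.
- **Other renal tests.** For haematology, chemistry and urinalysis the note says "Sample to be drawn pre-dose on Days 2, 4, 6, 8 and 10". The row is also marked on Day 12 and at follow-up.
- **Non-clinical background.** The risk table (Protocol 3.3.1) reports an adverse kidney tubule lesion in female rats after 28 days at 400 mg/kg/day. It adds: "This lesion was not seen in 7-day rat studies nor in monkey toxicology studies of" 21 days or less.
- **Adrenal comparison.** The same table calls the rat adrenal finding non-adverse. Even so, it plans adrenal testing in Part B before the first dose and again once the 10 days are complete, with cortisol on Day 11.
- **Analysis.** SAP 10.6.3 takes the renal biomarkers into the final analysis, with KIM-1 and NGAL corrected for urine creatinine. The displays that name them are Listings 52 and 53.

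**The concern.** The kidney is the first risk in the protocol's table, and the renal safety panel's advice set the exposure limits for both parts (Protocol 8.1.1). KIM-1, NGAL and urinary albumin are the scheduled tests chosen specifically to show tubular injury. In Part A the second sample, on Day 2, comes after the whole exposure of that period, which is a single dose. In Part B the second sample comes less than halfway through.

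Part B is meant to support the intended treatment duration and to inform longer studies (Protocol 5.4). Progression to the next repeat-dose cohort requires 10 days of dosing in at least four participants (Protocol 5.6.3). When that decision is taken, the latest scheduled injury-marker value is from Day 5 pre-dose. An effect that emerged between Day 5 and Day 10 could appear on these markers only if some other test or symptom had already prompted an unscheduled sample.

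**Working it through.** **1. Reading the schedule columns.** The table came through text extraction, so the column positions were checked against rows that state their own days. In the protocol's Part B table:
- The chemistry/urinalysis row decodes to Screening, Day -1, Days 2, 4, 6, 8, 10, 12 and follow-up. Its note names Days 2, 4, 6, 8 and 10, so it agrees.
- The cortisol row decodes to Days -1 and 11. Its note says the same.
- The treatment row decodes to Days 1 to 10, as stated elsewhere.
- By the same count, the biomarker row decodes to Days 1 and 5.

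The SAP copy (10.2.2) shows the same two biomarker marks. It is weaker support, because by the same count its cortisol mark falls on Day 10, against its own note of Day 11. The reading rests on the protocol table.

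**2. Dosing covered by the last scheduled sample.**
- Dosing days before the Day 5 morning dose: 5 − 1 = 4 of 10.
- Twice-daily doses before it: 4 × 2 = 8 of 10 × 2 = 20, which is 40%.
- Doses after it: 20 − 8 = 12, which is 60%, over 6 dosing days.
- With three doses a day the split is the same: 12 of 30, or 40%.

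**3. What continues after Day 5.** Protocol Table 7 and the schedule give, on Days 6, 8, 10, 12 and at follow-up:
- serum creatinine and phosphate;
- specific gravity, urine pH, dipstick protein and blood, urine creatinine and urine phosphate;
- microscopy if blood or protein is abnormal, and a protein:creatinine ratio if trace protein is found.

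The renal withdrawal criteria (Protocol 8.1.3) use these tests and not KIM-1 or NGAL.

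**4. How far the rat data go.**

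| | Lesion seen | 7-day rat study with a stated AUC |
|---|---|---|
| Duration | 28 days | 7 days |
| Sex | Female | Male |
| Formulation | Spray-dried dispersion | Free base |
| AUC (µg.h/mL) | 1290 | 26.8 to 273 |

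The highest 7-day AUC is 273/1290 = 0.21 of the AUC at which the lesion was seen. Duration therefore changes together with sex, formulation and a nearly five-fold difference in exposure (1290/273 = 4.7).

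**5. Expected exposure in Part B.** The repeat-dose AUC limit is 434/5 = 86.8 µg.h/mL, which reproduces the protocol's figure. The lesion AUC is 1290/86.8 = 14.9 times that limit and 1290/434 = 3.0 times the NOAEL AUC.

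**The case against.** The strongest case against is that this is a sampling-time preference, not an error. No passages contradict each other. The tests behind the renal withdrawal rules run to the end, and specific gravity and urine pH, which moved with the rat lesion, are among them. Extra biomarker samples are allowed, and time points can be added without an amendment. KIM-1 and NGAL enter no stopping rule, and exposure is capped about 15-fold below the level at which the lesion occurred. All of this stands, and it keeps the point modest.

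Three stronger readings are tempting, and the documents do not support them:
- *A reader might infer that renal monitoring ends at Day 5.* It does not; only the scheduled injury markers do.
- *A reader might infer that the rat studies show the lesion needs more than 7 days, so that Day 5 is uninformative.* The contrast is confounded, as shown above. Taken literally, it would also count against a Day 11 sample, since 10 days is nearer to 7 than to 28. The case for an end-of-dosing sample rests on covering the full course given, not on a proven delay.
- *A reader might infer that the Day 5 sample should be moved.* Sentinel participants are reviewed after five days of dosing, before the other six start (Protocol 5.1, Part B). Day 5 is the only scheduled on-treatment biomarker sample near that review.

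Discretionary sampling does not fill the gap. It is triggered by other findings, so it would give values from selected participants and no planned comparison of active with placebo.

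**Conclusion.** The point holds as a modest design improvement. The schedule contains no injury-marker sample for the last 6 of 10 dosing days (12 of 20 doses) or afterwards, and the documents give no reason for ending at Day 5. The adrenal finding, which the protocol regards as non-adverse, does get an end-of-course test.

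The 40/60 split counts doses. It equals a split of cumulative exposure only if each dose gives similar exposure, which fits the protocol's statement that simulations show no evident accumulation. The conclusion also assumes that the protocol table's columns were extracted correctly, which the chemistry, cortisol and treatment rows support. The documents do not show that participants are left without renal monitoring, nor does the plan claim 10-day renal safety from these markers. The loss is a planned reading over the full course in up to 18 active and 6 placebo participants (3 cohorts × 6 and 3 × 2). It would be descriptive only.

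**What to change.** Keep the Day 5 sample. Add one scheduled first-morning void on Day 11, or with the Day 12 urinalysis, assayed for KIM-1, NGAL, albumin and urine creatinine (the denominator of the SAP's KIM-1 and NGAL correction). Include the new time point in Listing 53, and add a descriptive summary of change from Day 1 by treatment.

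The Day 11 void needs care because of the Day 10–11 metabolism collection, where "All urine from each participant will be collected from 0-24 hrs post dosing". A pooled 24-hour specimen is not comparable with a single morning void. If the void falls inside the collection window, record its volume and take the aliquot before pooling, so that amount excreted, fraction excreted and renal clearance are unaffected. The handling details belong in the Study Reference Manual, which is not among the documents.

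The cost is one more urine assay for up to 24 participants and minor handling. Protocol 2.2 lets time points be added with documentation and approval and without an amendment. If the sponsor prefers not to add the sample, a stated reason why Day 5 suffices should go into the protocol.

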## 4. OBJECTIVES AND ENDPOINTS

Objectives	Endpoints
Primary	

 
To evaluate the safety and tolerability of single and repeat doses of GSK3186899 in healthy participants
 
	
 
Adverse event reporting, clinical laboratory safety data, vital signs, 12 lead ECGs, 24 hr telemetry.
 

Secondary	
 
To evaluate the systemic PK profile of single (fasted and fed) and repeat doses of GSK3186899 in healthy participants
 
 
 
Plasma concentrations of GSK3186899 plus derived parameters, as data allow. For SAD part: Derived PK parameters for GSK3186899 following single dose (fasted and fed) including area under the plasma drug concentration versus time curve (AUC(0-t), AUC(0-∞), maximum observed plasma drug concentration (Cmax), time to maximum observed plasma drug concentration (Tmax), trough plasma concentration (Ctau) and apparent terminal half-life (T1/2) as data allow. Predicted
 

Objectives	Endpoints

 
• To examine dose proportionality following single and multiple doses of GSK3186899
 
• To assess accumulation and time-invariance ratios of GSK3186899 after multiple doses
 
	
accumulation Ratio (ARpred)# will be calculated.
 
For MAD part: AUC(0-t), AUC(0-∞), AUC(0-tau), Cmax, Tmax and T1/2.
 
 
• Dose-proportionality assessment using derived PK parameters, as data allow:
 
 
For SAD part: AUC(0-∞), Cmax
 
For MAD part: AUC(0-tau), Cmax, Ctau
 
 
• Accumulation ratios assessment*, where data allow: RAUC(0-tau), RCmax, RCtau.
 
• Time-invariance ratio calculation as AUC(0-12) on day 10 to AUC(0-∞) on day 1.
 

Exploratory	

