Study Treatment				X	X	X	X	X	X	X	X	X	X				BID dosing: GSK3186899 or placebo will be administered using a 12hr dosing interval. If a different dosing regimen is used, refer to Appendix 5 of Protocol.

Procedure	Screening (Up to 28 days before Day 1)	Study Period (Days)													Follow-up (14-21 days post last dose) / Early Withdrawal	Notes	
		-2	-1	1	2	3	4	5	6	7	8	9	10	11	12		
12-Lead ECG	X		X	T	X		X		X		X		X		X	X	Vital signs to include HR, BP, temperature and respiration rate. BP will be conducted in both a supine and standing position if participant develops any signs/symptoms which in the investigators opinion are suggestive of adrenal insufficiency. 12-Lead ECG and Vital Signs to be conducted on Day-1 and pre-dose Day 1 and then at the subsequent time points post first-dose: 30 min, 1 hr, 1.5hr, 2hr, 2.5hr, 4hr, 6hr, 13hr and 14hr For Days 2-10: pre-dose assessments only. Timings will be reviewed as cohorts progress and may be adjusted to ensure appropriate measurements relative to peak concentrations for subsequent cohorts If a different dosing regimen is used, refer to Appendix 5 for alternative ECG and Vital Signs time-points. T = Triplicate (for all assessments except temperature and respiratory rate). If any abnormal ECG reading is recorded, refer to Section Error! Reference source
Vital signs	X		X	T	X	X	X	X	X	X	X	X	X	X	X	X	

Procedure	Screening (Up to 28 days before Day 1)	Study Period (Days)													Follow-up (14-21 days post last dose) / Early Withdrawal	Notes	
		-2	-1	1	2	3	4	5	6	7	8	9	10	11	12		
																	not found. of protocol for appropriate action.
PK Blood sampling																	
PK samples will be collected pre-dose and at the following time points post first-dose:
 
Day 1: 10min, 30min, 1hr, 1.5hr, 2hr, 2.5hr, 3hr, 4hr, 5hr, 6hr, 8hr, 10hr, and 12hr
 
Days 2 – 9: Pre-dose PK samples collected for each dose
 
Day 10: PK samples will be collected pre-dose and at the following time points post first-dose: 10min, 30min, 1hr, 1.5hr, 2hr, 2.5hr, 3hr, 4hr, 5hr, 6hr, 8hr, 10hr, and 12hr.
 
The time points stated may be modified depending on emerging SAD PK profiles. If a different dosing regimen is used, refer to Appendix 5 of Protocol for alternative PK blood sampling time-points.
 
Blood volumes to be collected include:
 
 • 2 mL for post-dose 0-11 hrs, and • 5 mL for post-dose 12-24 hrs (Days 1 and 10).

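### From Day 3 to Day 10, Part B schedules no ECG, vital sign or telemetry reading near peak concentration, and none is paired with the Day 10 PK profile

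*Protocol*

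**What the plan says.** The Part B schedule (Protocol 2.2) takes ECGs and vital signs serially after the first dose on Day 1, ending with "2.5hr, 4hr, 6hr, 13hr and 14hr". Doses are given "using a 12hr dosing interval", so the last two of those readings are 1 h and 2 h after dose 2. For Days 2-10 the instruction is "pre-dose assessments only". In the grid that means ECGs on Days 2, 4, 6, 8 and 10 and vital signs daily. Readings after Day 10 follow the end of dosing. SAP 10.2.2 repeats this schedule.

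Telemetry is marked on Days 1 and 2 and described as "Continuous at least 24 hr post-evening dose". PK sampling is different: "Day 10: PK samples will be collected pre-dose and at the following time points post first-dose" (SAP 10.2.2), at times that include 1, 1.5, 2 and 2.5 h. Appendix 5 also limits ECGs and vital signs to pre-dose on Days 3-10 for once-daily and three-times-daily dosing, again with a PK profile on Day 10.

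The primary endpoint for repeat dosing (Protocol 4) covers adverse events, laboratory data and "vital signs, 12 lead ECGs, 24 hr telemetry". The schedule adds that timings "may be adjusted to ensure appropriate measurements relative to peak concentrations for subsequent cohorts".

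**The concern.** Repeat-dose safety is a primary objective, and the reason to dose for 10 days rather than one is to see what changes with time. Yet after the first two days the only scheduled cardiac and haemodynamic readings on treatment are troughs of a drug with a predicted half-life of about 1.3 h.

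Three uses of the data depend on those readings:

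- **Escalation.** The decision to open Cohort 5 or 6 follows 10 days' dosing in at least four participants and reviews adverse events, laboratory tests, ECGs and vital signs (Protocol 5.6.3). Telemetry is named in the Part A list (5.6.2) but not here.
- **Sentinels and QTc withdrawal.** The five-day sentinel review cites vital signs and ECGs (5.1). The QTc criteria (8.1.6) start from an ECG showing prolongation. From Day 2 the scheduled ECGs can show that only at trough.
- **Reporting.** SAP Tables 3.30 and 3.32 (change from baseline in ECG and vital signs, Part B) will hold trough values from Day 2 to Day 10, with no near-peak comparison of Day 10 with Day 1.

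**Working it through.** **Inputs.** Protocol 5.5.1 and Table 3: CL 438 mL/h/kg (CV 50%), V 800 mL/kg (CV 30%), KA 0.7 per h (CV 10%), F 50%. Dosing interval 12 h (2.2). For the check against Table 5: 70 kg and a blood-to-plasma ratio of 0.60. Model: one compartment, first-order absorption.

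**Reproducing the plan's figures.** k = 0.438/0.8 = 0.5475 per h, so the half-life is 0.693/0.5475 = 1.27 h, against about 1.3 h stated in Protocol 5.4. AUC = F × dose/(CL × 70)/0.60. At 30 mg this is 0.5 × 30/30.66/0.60 = 0.815 µg.h/mL, against 0.82 in Table 5. At 600 and 2500 mg it gives 16.3 and 67.9, against 16.59 and 68.72. Cmax for a typical subject comes out about 13% above Table 5 (3.70 against 3.28 µg/mL at 600 mg); Table 5 gives simulated means.

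**Time of peak.** Single-dose tmax = ln(0.7/0.5475)/(0.7 − 0.5475) = 1.61 h; at steady state it is 1.60 h.

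**Trough as a share of peak.** At steady state C(t) is proportional to e^(−kt)/(1 − e^(−12k)) − e^(−KA·t)/(1 − e^(−12KA)).

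- Pre-dose: 1.00140 − 1.00022 = 0.00118.
- Peak, at 1.60 h: 0.4162 − 0.3256 = 0.0907.
- Ratio: 0.00118/0.0907 = 1.3%, or about 1.5% against the Table 5 Cmax.

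Drawing 32,000 subjects with the Table 3 CVs (log-normal, fixed body weight) gives a median of 1.4% and a 5th-95th percentile range of 0.08% to 17%.

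**Post-dose readings as a share of steady-state peak:** 91% at 1 h, 99.8% at 1.5 h, 97% at 2 h. The Day 1 readings at 13 h and 14 h therefore sit at about 91% and 97%.

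**Coverage over 20 doses (10 days, twice daily).** ECG and vital signs are near peak after doses 1 and 2. Telemetry must run to at least 12 + 24 = 36 h after dose 1. Dose 3 is at 24 h and peaks at about 25.6 h, so that peak is covered; dose 4 is due at 36 h. Doses 4 to 20, 17 of the 20, have no scheduled near-peak cardiac or haemodynamic reading.

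**If the half-life is longer than predicted (assumed values):**

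| Half-life | Trough as % of peak | Cmax accumulation |
|---|---|---|
| 1.27 h (Table 3) | 1.3% | 1.006-fold |
| 2 h | 6% | 1.03-fold |
| 3 h | 16% | 1.10-fold |
| 5 h | 33% | 1.30-fold |

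**Appendix 5.** Once daily, the pre-dose level is about 0.002% of peak. With three doses at 7 h intervals the overnight gap is 24 − 14 = 10 h, and the level 10 h after a single dose is 3.6% of its peak.

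**The case against.** A reader might infer that the primary endpoint has no near-peak reading at all after repeat dosing. The documents do not support that. ECGs and vital signs are taken 1 h and 2 h after dose 2, telemetry spans the dose 2 and dose 3 peaks, and adverse events, also part of the endpoint, are reviewed throughout.

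The strongest defence goes further. The model that puts the trough at 1.3% also predicts almost no accumulation, with the dose 2 peak above 99.9% of the steady-state peak. Protocol 5.5.2 likewise finds no accumulation in simulation. For parent drug, then, Day 1 already samples the Day 10 peak. Part A takes ECGs and vital signs densely after single doses, under a higher Cmax ceiling (15.4 against 9.24 µg/mL, Protocol 8.1.1). The risk table names kidney, stomach and adrenal effects, not a cardiac one. A metabolite that built up over days would still be present at trough, so the pre-dose readings are not blind to it.

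All of that stands, and it limits the harm. It does not close the gap. Matching concentrations on Days 1 and 10 does not imply matching responses if an effect develops with time. Accumulation and time-invariance are secondary objectives, so the study itself treats them as open. SAP 2.3 records that dose level 7 was not given because exposures were higher than expected. That does not show a longer half-life, but it weakens reliance on predicted PK.

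The timing clause helps only in part. "Timings will be reviewed as cohorts progress and may be adjusted" is a permission, and it commits to no reading.

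**Conclusion.** The gap is real but narrow. From Day 3 to Day 10 no ECG, vital sign or telemetry reading is scheduled near peak, and none accompanies the Day 10 PK profile. Under twice-daily dosing the pre-dose readings fall at about 1.3% of predicted peak in a typical subject, with a 5th-95th percentile range of about 0.1% to 17%.

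What could be missed is a peak-related cardiac or blood pressure effect that appears only after several days, or one that follows more accumulation than predicted. The two routes differ. With real accumulation the trough is no longer near 1%, so pre-dose readings would carry more information, though still well below peak.

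The percentages rest on a one-compartment model with predicted parameters and should be recalculated from Part A data. The scheduling gap itself does not depend on the model. This is a change the sponsor should make, not a defect that undermines the primary objective.

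**What to change.** - Re-time the Day 10 ECG and vital signs from pre-dose to about 1.5-2 h after the morning dose, where PK is already drawn. Adjust the time to the tmax observed in Part A under the food condition chosen for Part B.
- In the SAP, add a descriptive summary of Day 10 against Day 1 at the matched time, by dose and placebo. With six active participants per cohort it should carry no formal test.
- Use the same number of replicates on both days. The grid marks Day 1 as triplicate, while Protocol 9.1.2 describes triplicate vital signs only before the dose, so state which applies to the post-dose Day 1 readings.
- Make the same change in Appendix 5 for once-daily and three-times-daily dosing, where Day 10 PK is also drawn at 1.5 and 2 h.

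**Cost.** One fewer trough reading. Trough ECGs remain on Days 2, 4, 6 and 8 and trough vital signs daily through Day 9. No visit or blood draw is added, and Protocol 2 allows a documented timing change without an amendment. If Day 10 has to be triplicate to match Day 1, that means two further tracings and readings. If the last on-treatment trough is thought worth keeping, the post-dose reading can be added instead, at the cost of one more ECG and vital-sign set per participant.
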